Process and outcome measures: Patient-level data will be extracted about the process and outcomes of care for the eligible cohort of patients before and after implementation of the template. This will include details of whether patients were invited for a long-term conditions review, whether they attended, the level of completion of different aspects of the review, number of drugs prescribed, number and duration of consultations in primary care, and indicators of clinical control eg BP, HBA1C). All of this data will be extracted in pseudonymised form from the computer system and only identified by a pseudonymised ID from which the research staff cannot identify individual patients. This pseudonymised ID is a long alphanumeric code generated automatically by the EMIS software, and not the same as the patient's EMIS number which is the standard identifier used within EMIS practices. We will ensure that no features are included which raise a risk of identification e.g. we will use age-group and month of birth rather than date of birth, deprivation decile rather than post code, and will only include details of common long-term conditions so that patients cannot be identified through having a particular rare condition. Details will be collected for the period from 1 April 2021 to 31 March 2023.

We will collect fully anonymised data about the number of adult patients with whom the template was used, and the age and long term conditions of those patients, whether or not they are included in the

cohort of patients with multimorbidity. This is to explore the extent to which practices use the template in patients with long-term conditions who are not included in the multimorbidity cohort, including, for example, those with single conditions.

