The aim is that healthcare practitioners in the participating practices will use the new template with any patient with multimorbidity having an annual review. Some practices may also choose to use it with patients having a review for a single condition, but these patients will not be included in this study. Some practices may decide not to use the template with all eligible patients, but will choose to start with a particular group of patients. We will be flexible in working with practices and the decisions about how they choose to use the template are one item of interest in the qualitative evaluation.

Practices will use their usual procedures to invite people for review. In many practices this is done using the patient's month of birth (so that patients with a birthday in June are invited for review each June) and we will encourage this approach.

We will collect anonymous routine data for the variables previously described for all patients meeting the eligibility criteria, and we will invite up to 4800 patients (an average of 200 patients per practice) to provide patient reported outcome data. Depending on the number of practices recruited, the number of eligible patients, and the response rate, we may invite more than 200 patients to complete the survey in some practices in order to reach our overall recruitment target.

We will purposively sample patients to take part in interviews and observation of their consultations, seeking to ensure maximum variability in terms of age, gender, ethnicity, and number and type of long-term conditions. We will aim to observe and interview patients and healthcare practitioners after a

mix of initial consultation and annual review consultations, and include both in-person and virtual consultations. We will aim to observe and interview a range of healthcare practitioners (healthcare assistants, nurses, GPs), some who are newer to using the template, and some who are more familiar with it, to better understand processes of normalisation. We will regularly review the profile of patients already recruited and use this to inform decisions about which patients to recruit subsequently.

Size of sample

We anticipate collecting qualitative data from the following numbers of individuals. Please note that we are over-sampling the qualitative data collected in the three Maxwell practices receiving the Year of Care training in order to understand their experience of that training and its impact on the use of the template.

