researchers and with input from the PPI contributors, each transcript will be coded by one researcher and a sample of these transcripts will be reviewed independently by a second researcher. The thematic analysis²⁶ will be conducted by the small team of three members of research staff who conducted the interviews. These researchers will initially identify themes, which will then be discussed with other members of the research team and the PPI groups. The audio/video-recorded consultations will also be fully transcribed and analysed thematically, as described above. An observation guide will support analysis of the fidelity of use of the template. In addition to assessing fidelity, we will analyse the recordings of consultations to look for evidence of having received training, considering the variation in training and how this may have affected the practices' experience of, and approach to, using the template and patients' experience of the reviews. We will also look for evidence of use of person-centred consultation skills.

The routine data will be used to understand the adoption, reach and fidelity of implementation. This will include exploring the proportion of eligible patients who were invited to a review, the proportion that attended, and the extent to which key elements of the template were completed. We will also explore whether there are particular patient groups who were more or less likely to receive a complete review as intended. As far as possible, the quantitative analysis will include the items specified within the Finance, Commissioning and Contracting Handbook for Personalised Care (e.g. % eligible people receiving a personalised care plan, % referred to social prescribing link-workers).²⁷

In the pre-intervention period, most patients will have been invited to an annual review consultation based on a pre-existing template, but this would rarely lead to provision of a care and support plan. The intervention consists of patients being invited for an annual review using the new template, which encourages provision of a care and support plan. Over the study time period, the number of eligible patients being invited for an annual review consultation based on the new template (the intervention) should increase. Some of these patients will receive a care and support plan (the primary outcome).

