We will estimate implementation and delivery costs of the annual review intervention, and explore the wider impact on healthcare resources, from an NHS perspective. We will explore the possibility of including social care data as well, depending on the availability of linked data. The implementation

cost per GP practice will include administration and practice staff training to deliver the annual review intervention. The delivery cost per patient will include staff time, medication costs and investigations associated with delivering the annual review, and any further healthcare contacts instigated during the review.

Impact on wider healthcare resource use: in addition to the implementation and delivery costs, the intervention may lead to changes in healthcare use (e.g. (i) at an aggregate level, (ii) between primary and secondary care, or (iii) between elective and emergency care). We will use regression models to compare measures of healthcare cost during the postintervention period for patients who received the intervention and those who did not, in intervention and control practices. The post intervention period will be defined as the month of the patients' birthdate to the end of the data collection period. Models will account for baseline healthcare costs (those in the same period in the previous year) and patient and practice characteristics.

As described above, anonymised primary care data, including consultation duration, will be collected from practices' EMIS software (either directly by each practice, or via a system wide dataset), and we will seek to collect secondary care data from a system wide data set where available or the NHS Secondary Uses Service (SUS). Administration costs and time for practice staff training will be estimated from data collected by the research team. Staff time and medication costs will be based on national estimates,^{29,30} and investigations will be costed using national estimates²⁹ or literature. Secondary care data will be costed using national tariffs.³¹

10) ETHICAL AND REGULATORY CONSIDERATIONS

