Given that the eligible cohort all have multiple long term conditions, and many of them will be elderly and frail, we expect a high rate of events such as hospitalisations and deaths which are not related to the implementation of the template. We will investigate any serious adverse events (SAEs) which anyone involved with the study reports could be related to the intervention or the research procedures, whether reported by patients, practice staff or researchers. Details will be collected using an adverse events form, and a register will be kept of all events investigated and how they were resolved. The Chief Investigator is responsible for defining each event in relation to its seriousness, relatedness and expectedness.

A Serious Adverse Events (SAEs) is defined as an event that:

- results in death;
- is life-threatening;
- requires hospitalisation or prolongation of existing hospitalisation;
- · results in persistent or significant disability or incapacity; or
- consists of a congenital abnormality or birth defect; or
- is otherwise considered medically significant by the investigator.

SAE reporting is handled via a Service Level Agreement with University Hospitals Bristol and Weston NHS Foundation Trust. SAEs that are related to the study (ie they resulted from administration of any of the research procedures) and unexpected (ie not listed in the protocol as an expected occurrence) will be reported to the sponsor within 3 working days and emailed to the REC using the Non-CTIMP safety report to REC form within 15 days of the chief investigator becoming aware of the event.

Any urgent safety matters will be reported to the sponsor and REC immediately by telephone and email and confirmed in writing within 3 working days.

Data protection and patient confidentiality

All investigators and study site staff will be required to comply with the requirements of the Data Protection Act 1998 and GDPR with regards to the collection, storage, processing and disclosure of personal information and will uphold the Act's core principles.

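### The wider cost analysis groups patients by whether they received the intervention, which exposes it to selection and immortal-time bias of unknown sign; the main contrast should be by practice arm

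*Protocol*

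**What the plan says.** The last part of *Data analysis* in Section 9 of the protocol covers the impact on wider healthcare resource use. Regression models will compare "healthcare cost during the postintervention period for patients who received the intervention and those who did not", in intervention and control practices. On timing: "The post intervention period will be defined as the month of the patients' birthdate to the end of the data collection period". The models adjust for cost in the same period of the previous year and for patient and practice characteristics.

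Other parts of the protocol bear on who receives the intervention and when:

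- **Definition** (Section 9, *Data analysis*): "The intervention consists of patients being invited for an annual review using the new template". The same section goes on to treat attendance and completion of the review as separate steps.
- **Practice choice** (Section 9, *Patient and staff sampling*): "Some practices may decide not to use the template with all eligible patients", and may begin with one patient group.
- **Timing of invitation** (same place): "Practices will use their usual procedures to invite people for review". Many practices recall by month of birth, and the study encourages this without requiring it.
- **Clinician choice** (Section 10, opening paragraphs): use of the template is left to the consulting clinician.
- **Expected events** (Section 10, *Protocol compliance*): "we expect a high rate of events such as hospitalisations and deaths".
- **Data period** (Section 9, *Routinely collected data*): "Details will be collected for the period from 1 April 2021 to 31 March 2023".

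The primary outcome is handled differently. It is compared by practice arm, with period, their interaction and a random practice effect.

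**The concern.** Receipt is settled after follow-up begins and by people who can see the patient's current health. Two problems follow.

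1. **Selection.** If practices, clinicians or patients sort themselves by present health, recipients and non-recipients differ in expected cost whatever the template does. Prior-year cost measures past health with noise and says nothing about deterioration since.
2. **Immortal time.** Follow-up starts in the birth month, but a patient becomes a recipient only if a review (or an invitation, if that is the meaning) follows. Anyone who dies or leaves first is a non-recipient by construction, and any terminal cost is booked to that group.

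At stake is the economic message. Cost is a named dimension of the evaluation, and the results are meant to inform wider implementation. A contrast by receipt could show a saving or an extra cost that reflects who was reviewed.

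**Working it through.** The protocol gives no sample size, effect or power for the cost analysis, so there is no figure of its own to reproduce. Its cohort size is consistent: 24 practices × 300 patients = 7200 per arm.

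**Length of the window.** If the post-period year runs from April 2022 to March 2023, an April-born patient contributes 12 months and a March-born patient 1 month. The mean is (12 + 11 + … + 1)/12 = 78/12 = 6.5 months. A review a few months after the birth month therefore takes up a large part of the window.

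**Simulation with a true effect of zero.** The size, window and type of adjustment follow the protocol. The remaining inputs are assumptions.

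- 48 practices × 300 = 14,400 patients; half the practices are intervention practices; the two arms are generated alike.
- Each patient has a persistent frailty score F and a new deterioration score S, both standard normal. Mean monthly cost is proportional to exp(0.5F) in the prior year and exp(0.5F + 0.5S) afterwards.
- Deaths follow a base hazard of 4% a year multiplied by exp(0.6F + 0.8S), giving about 3.4% dead within the window. A terminal cost of 4000 is added (base monthly cost 100).
- The review falls 0 to 4 months after the birth month. The log-odds of having it are 0.3 + b(F + S), with b = ±0.2 (mild) or ±0.5 (strong). About half of intervention patients are recipients.
- Model: post-period cost = a + β₁ × same-period prior-year cost + β₂ × number of conditions + β₃ × window length + δ × group. The table gives δ divided by mean cost, averaged over 60 replicates.

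| Scenario | Recipients v non-recipients, intervention practices | Recipients v all non-recipients | All patients by arm |
|---|---|---|---|
| No selection, no deaths | +0.9% | +1.1% | +0.6% |
| No selection, deaths, no terminal cost | +1.5% | +0.9% | −0.1% |
| No selection, deaths with terminal cost | −7.0% | −4.7% | −0.2% |
| Healthier reviewed, mild | −23.6% | −15.5% | −0.2% |
| Healthier reviewed, strong | −45.3% | −29.8% | −0.2% |
| Sicker reviewed first, mild | +9.2% | +5.8% | −0.2% |
| Sicker reviewed first, strong | +29.3% | +19.1% | −0.2% |

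The replicate SD of the by-arm estimate is about 4 to 5%. Its Monte Carlo standard error is therefore about 4.4/√60 ≈ 0.6%, and the last column is consistent with zero throughout.

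**Effect of recorded characteristics.** A second type of null model assumes 15% frail patients with 5 times the monthly cost and monthly death of 2% v 0.2%. With 45% of frail and 75% of other patients attending, and adjustment for prior-year cost and window length, the spurious saving is 15% to 32%, depending on how noisy individual costs are assumed to be. In the version giving 15%, adding a frailty indicator cuts it to about 2%. With frail patients attending more often (90% v 60%), the result is +12% without the indicator and −1% with it. When receipt is taken to mean invitation, the contrast is about −2%.

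**The case against.** The strongest defence has four parts.

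- **Planned adjustment.** The model includes patient and practice characteristics, and severe frailty and dementia are among the recorded cohort conditions. As shown above, this removes most of the bias when selection runs through those records. It does not deal with unrecorded or recent deterioration, or with the misaligned clock.
- **Meaning of received.** By the protocol's own definition the intervention is the invitation. On that reading attender bias largely goes. Selection into invitation, and the gap between birth month and invitation, remain.
- **Eligibility.** Patients not normally called for review, such as some with terminal illness, are excluded. This reduces the problem without ending it.
- **Control practices are in the model.** How arm and receipt enter together is not stated, and a statistical or health economics plan may settle it. The sentence nonetheless names receipt as the contrast. Nor are receipt and arm interchangeable: control practices may subscribe to Ardens, and the template was released to all subscribers.

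Some stronger readings are tempting but unsupported. A reader might infer that the analysis will manufacture savings because healthier patients attend. Practices and clinicians may equally put sicker patients first, which reverses the sign. A reader might infer that birth-month recall is uncommon; the protocol says many practices use it, and Section 7 describes it as the intended timing. Nor was the control arm added to prevent this bias: the version history says it replaces a before-and-after comparison. Finally, the clinical-indicator analyses state no contrast by receipt, so the point does not extend to them.

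**Conclusion.** The concern holds for the wider cost analysis. As worded, its contrast rests on a selected, post-baseline grouping, with a clock that starts before receipt is known. The bias has no sign that the documents fix. In the main zero-effect simulation it ranged from −45% to +29% of mean cost within intervention practices, and from −30% to +19% against all non-recipients. Those sizes depend on assumed strength of selection, mortality and terminal cost, for which the protocol gives no figures. They would shrink to a few percent if selection ran wholly through recorded characteristics or if received means invited. The near-zero result by arm depends on arms generated as comparable; the real practices are not randomised.

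The analysis is secondary and described as exploring wider impact. The primary outcome is already compared by arm and is unaffected. The wording should be changed, but the point does not threaten the study's main result.

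**What to change.** - **Main contrast.** Compare all eligible patients in intervention practices with all eligible patients in control practices, regardless of receipt. Use the arm-by-period frame of the primary analysis, with a random practice effect and the planned patient and practice characteristics. Prior-year same-period cost enters once, either as the earlier-period outcome or as a covariate.
- **Clock.** Keep the birth-month start already specified, "birthdate to the end of the data collection period", identically in both arms. Retain patients who die or leave, with their cost and person-time up to exit.
- **Receipt.** State whether received means invited or attended. Report received versus not received as exploratory only, with a note that its bias has no known sign.

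This changes wording only, since the same routine data are already to be collected in both arms. The price is dilution: patients who are never reviewed, and time before review, pull the estimate towards no difference. That estimate answers what introducing the template does to cost across the eligible population. Because practices are not randomised, baseline adjustment is still needed and some confounding between practices may remain.

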Implementation will be evaluated in a study using mixed qualitative and quantitative methods. The aim is to evaluate implementation and effectiveness of the intervention using a realist approach (how does it work, for whom, in what circumstances). The evaluation of the implementation will be examined using Normalisation Process Theory (NPT) as a theoretical evaluation framework. Participating CCGs will encourage implementation amongst all practices in their area but we will collect data in about 24 'beacon' practices (8 in each area).
In a nested sub-study, three practices in deprived areas of Bristol will receive additional support and training to change the way they manage patients with multimorbidity, including the template. This will make it possible to examine the impact of the template alone or as part of a wider practice change.
The evaluation will use concurrent mixed-methods to obtain evidence about intervention acceptability, feasibility, adoption, fidelity, cost, reach and sustainability. Data collected in the first few practices will be used formatively to improve future roll-out.

	 Data sources will include the following, collected in about 24 'intervention' practices (arm 1) from patients with two or more long term health conditions and eligible for an annual review: Interviews with patients Video-recorded observations of consultations Interviews with staff NPT NOMAD questionnaire for clinical staff Anonymised routinely collected data about numbers of patients receiving each intervention component Patient reported outcome measures based on survey before and after review Routinely collected data will be collected in about 24 'control'
	practices (arm 2) who have not been actively encouraged to use the template, for comparison purposes. In both intervention and control practices, data will be collected from 1 April 2021 to 31 March 2023, including periods before and after introduction of the template.
	This project will provide evidence to inform wide-spread implementation of a 'whole-person' review for patients with multimorbidity in line with the NHS Comprehensive Model for Personalised Care.
Study Participants	Patients aged 18 or over with two or more long term health conditions eligible for an annual review of their conditions

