There is increasingly interest within the NHS in using patient-reported outcome measures in the context of routine care, to inform clinicians about the needs of individual patients and as a quality improvement method, rather than as research tools. We will seek to implement this principle by asking patients to complete a brief patient-reported outcome measure before and 2 months after their annual review consultation. We view this as part of the intervention rather than as a research tool. We will send practices regular reports about aggregate results from their patients' responses, so they can identify problems and/or improvements over time in, for example, whether patients thought their care was well co-ordinated. We will ask patients to complete the Person-Centred Coordinated Care Experience Questionnaire (P3CEQ).²⁰ Practice administrative staff will send patients the initial questionnaire when they send their appointment for their multimorbidity review. Patients will be asked to return their questionnaire to the research team for analysis. The questionnaire will invite patients to give their consent to the research team sending them a follow-up questionnaire 2 months after the consultation.

Routinely collected data

These data will be used in three ways.

Cohort details: First, details will be extracted from the computerised record system within each participating general practice. Full anonymous data will be provided about the total number of patients in the practice, and the number meeting the eligibility criteria by age-group. The eligible patients form the cohort for the study. We will collect pseudonymised data about the characteristics of the cohort, including the number with each of the chronic diseases which define the eligibility criteria (see page 23), their age-group, month of birth, sex, ethnicity and deprivation (Index of Multiple Deprivation decile). Month of birth is necessary for the difference in difference analysis described later.

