Comparative analyses using the routinely recorded data will explore whether the primary outcome of receipt of a personalised care and support plan differs between patients in intervention and control practices. Negative binomial regression will be used to assess the number of patients receiving a plan in each practice in each time period (2021/22 vs. 2022/23), in a difference-in-difference analysis framework. Intervention (a binary variable indicating intervention or control practices), period (2021/22 vs. 2022/23), and the interaction between the two will be fitted as fixed effects, with practice as a random effect. As the same patients will appear in both time points, no adjustment for age, sex, etc is required. Whether the effect of year differs within particular patient groups will be explored by fitting the patient group variable (e.g. sex) as well as additional interactions, in the model, all as fixed effects.

A second set of comparative analyses will look at the impact on practice workload, including frequency, duration, and type of consultation, as well as the staff group who performed the consultation. Further, the number of regular reviews for specific diseases, and the number of fidelity type measures (e.g. mood and memory) and drugs prescribed will be explored, among other indicators. We will explore whether use of the template has any impact on clinical indicators of high quality care, such as blood pressure control or diabetic control. Subgroup analyses (e.g. exploring telephone consultations only) will be analysed as separate models for each subgroup of interest.

For all methods outlined, underlying assumptions in statistical models will be checked using standard methods, e.g. residual plots, etc. If assumptions are not valid, alternative methods of analysis will be sought.

The patient questionnaire will be used to quantify patient-reported outcomes before and after receiving the patient-centred multimorbidity review. Simple descriptive statistics will illustrate the health difficulties that patients with multimorbidity report most commonly. We will also explore whether there is a change in patient experience after the review, using similar models as described above.

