This is an implementation project which seeks to explore how best to implement a computerised template, and to study the impact of implementing the template. The template itself is already in use and this project aims to improve the template and to study how to improve its implementation, with a view to supporting the ultimate aim which is to improve the personalisation of care. In most respects this can be considered a service improvement project, but we are seeking NHS ethics approval because the study is designed to produce generalisable or transferable findings beyond those practices included in the study.

The intervention itself does not raise any risks for patients beyond usual care. The decision to use the template, and clinical decisions which are connected with use of the template, are entirely at the discretion of the clinician consulting with the patient.

The routinely collected data will be pseudonymised (linked anonymous) and identifiable only by the patient's clinical team, not by the research team. We will ensure that we do not collect data that could in combination have a significant risk of making the patient identifiable.

The patient and staff interviews or questionnaire survey do not raise any ethical issues beyond the usual requirement to obtain fully informed consent.

The collection of recordings of general practice consultations raises ethical issues. We have considerable experience of collecting this type of data, for example in the 'one in a million' project http://www.bristol.ac.uk/primaryhealthcare/researchthemes/one-in-a-million/. We will ensure that patients are fully aware of how their data will be stored and used and give fully informed consent as described under 'Consent' on page 22.

Assessment and management of risk

Potential risks from the study are described below. We will maintain a register which records details of any events of this type, how we responded and who we passed the information on to.

Risk Miti	igation
-----------	---------

We identify patients who appear to have serious medical problems which have not been addressed.	We will draw this to the attention of the GP within the practice responsible for the patient's care

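### The baseline cost covariate in the exploratory cost comparison shrinks from twelve months (April birthdays) to one month (March), so adjustment is needlessly weak for late birth months

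*Protocol*

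**What the plan says.** The rule is in Protocol section 9, Data analysis, in the paragraph on wider healthcare resource use. Costs are compared "for patients who received the intervention and those who did not, in intervention and control practices". The outcome window is set by birth month: "The post intervention period will be defined as the month of the patients' birthdate to the end of the data collection period". On adjustment: "Models will account for baseline healthcare costs (those in the same period in the previous year) and patient and practice characteristics".

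The extraction window is given under Routinely collected data ("Details will be collected for the period from 1 April 2021 to 31 March 2023") and again in the study summary for both arms ("In both intervention and control practices, data will be collected from 1 April 2021 to 31 March 2023"). Birth month is among the extracted variables: "Month of birth is necessary for the difference in difference analysis described later". Secondary care data are to be used only if they can be obtained.

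**The concern.** Who receives the intervention is not random. Section 10 leaves it to clinical judgement: "The decision to use the template, and clinical decisions which are connected with use of the template, are entirely at the discretion of the clinician". Section 9 also lets practices begin with a chosen group of patients. Recipients and non-recipients may therefore differ in their usual cost level, and baseline cost is the only adjustment variable that the paragraph names specifically.

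A covariate need not match the outcome window in length. Its job is to measure the patient's usual cost level, and one to three months of cost measures that less well than a year does. Under the stated rule the quality of the adjustment depends on when the patient was born, while months already in the planned extract go unused. Any confounding left over would be read as an effect of the review on cost.

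**Working it through.** The protocol gives no precision or sample-size figure for the cost comparison, so there is no figure of its own to reproduce.

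**Step 1: window lengths.** The birth month that starts the outcome must fall in 2022/23, because an earlier start would need baseline data from before 1 April 2021. Both windows then run from the birth month to March: April 12 months, October 6, January 3, February 2, March 1 (March 2022 only). If births are spread evenly, the mean is (12 + 11 + … + 1)/12 = 78/12 = 6.5 months. The share of the 2021/22 year left unused is 1 − 6.5/12 = 46%. Half of the birth months (October to March) have 6 months or fewer.

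**Step 2: what a shorter baseline does when it is a covariate.** Let ρ be the correlation between a patient's costs in two different months. The reliability of an m-month mean as a measure of the patient's cost level is R = mρ / (1 + (m − 1)ρ). Adjusting for that mean alone leaves about 1 − R of the confounding that runs through cost level. At ρ = 0.10:

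- 1 month: R = 0.10/1.00 = 0.10, leaving 90%
- 3 months: R = 0.30/1.20 = 0.25, leaving 75%
- 6 months: R = 0.60/1.50 = 0.40, leaving 60%
- 12 months: R = 1.20/2.10 = 0.57, leaving 43%

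The documents do not give ρ, so a range is needed. Share left by the baseline covariate alone:

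| Assumed ρ | March (1 month) | January (3) | October (6) | Full year (12) |
|---|---|---|---|---|
| 0.05 | 95% | 86% | 76% | 61% |
| 0.10 | 90% | 75% | 60% | 43% |
| 0.20 | 80% | 57% | 40% | 25% |
| 0.30 | 70% | 44% | 28% | 16% |

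**Step 3: effect on the pooled estimate.** A simulation with no true effect used 240,000 patients, even birth months, and receipt depending on cost level. It gave these shares of the unadjusted confounding left in the overall estimate:

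| Assumed ρ | Per-month cost: same-period vs full-year | Total cost with window-length indicators: same-period vs full-year |
|---|---|---|
| 0.05 | 88% vs 71% | 76% vs 70% |
| 0.10 | 77% vs 52% | 59% vs 52% |
| 0.20 | 60% vs 34% | 39% vs 33% |
| 0.30 | 47% vs 22% | 27% vs 22% |

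Here full-year cost replaces same-period cost. The gap is 17 to 26 points per month and 5 to 7 points for total cost. Adding full-year cost to same-period cost lowers the confounding left by about 22 to 26 and 6 to 9 points respectively. Together the ranges are 17 to 26 and 5 to 9 points. The protocol does not say which scale will be used.

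**Step 4: the other covariates.** The same sentence also adjusts for characteristics of the patient and the practice. Suppose (an assumption) that these remove half of the between-patient confounding. Over ρ = 0.05 to 0.30 the share left becomes 41–49% for March and 30–46% for January, against 14–38% with the full year. The direction is unchanged and the gap is smaller.

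**Step 5: weight of the late birth months.** January to March supply (3 + 2 + 1)/78 = 7.7% of follow-up person-months, and March alone 1/78 = 1.3%. This is why the total-cost estimate moves little.

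**The case against.** Four points can be made for the plan.

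**The model form is not fixed.** The paragraph says only that baseline cost will be accounted for. Section 9 ties birth month to a difference-in-difference analysis, and the cost paragraph is the only later analysis that uses birth month. A change score over equal, season-matched windows left about none of the confounding in a null simulation where receipt depended on a stable patient trait, whatever the window length. This stands as a condition on the point. Still, accounting for baseline cost alongside patient and practice characteristics reads most naturally as covariate adjustment.

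**The same-period window has a purpose.** It matches season and length of exposure and, where practices recall by birth month, position in the review cycle. This stands, and is a reason to keep that covariate. It is no reason to leave the other 2021/22 months unused.

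**The obvious remedy can do harm.** Replacing same-period cost with the annual total, under one common slope and a total-cost outcome, misfits short windows: the appropriate slope for March is about one twelfth of that for April, and a birth-month main effect does not alter slopes. In null simulations over ρ = 0.05 to 0.30 the March bias changed sign and reached roughly 1 to 4.6 times its unadjusted size. This stands and shapes the fix.

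**The analysis is exploratory.** It is not the primary outcome, and its secondary care costs depend on data access. This limits the importance of the point.

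A reader might infer that confounding is left largely uncorrected for late birth months. The documents do not support that. It would need a low ρ, which is not stated, and would ignore the other covariates. Nor do late birth months dominate the overall result, given their small share of person-time.

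**Conclusion.** The point holds in a limited form. The window arithmetic follows directly from the protocol. The rule is stated there, so it is not a detail left to an analysis plan. If baseline cost is a regression covariate, the adjustment is weaker for late birth months than the planned extract requires. Full-year cost does better at every ρ tried.

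For the overall estimate the loss is modest on a total-cost scale (about 5 to 9 percentage points more confounding left) and larger on a per-month scale (about 17 to 26 points). These figures rest on an assumed ρ of 0.05 to 0.30, even birth months and confounding through a stable cost level, and are before the other covariates act. With a change-score model there would be nothing to correct. It is worth changing because the comparison is confounded and the change is small; it does not invalidate the cost analysis.

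**What to change.** In section 9, Data analysis, in the paragraph on wider healthcare resource use:

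- Keep same-period cost in the model.
- Add each patient's mean monthly cost over 1 April 2021 to 31 March 2022 as a second covariate.
- Express outcome and baseline costs per month of follow-up, or scale the annual covariate by the length of the patient's outcome window. An unscaled annual total with one common slope should not be used with a total-cost outcome.
- Include birth month in the model.
- State whether baseline cost enters as a covariate or through a change score.

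For April birthdays the two baseline measures coincide, so nothing changes for them. The extraction needs no change. The price is one extra covariate and a rule for patients without a full 2021/22 record (for example, those who registered during that year) or without secondary care data. The outcome window for late birth months, down to one month for March, remains short; a longer baseline does not cure that and it needs its own decision.
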